#### Trial/Study Design

Study data for this analysis will be from the BEST Trial, which has been described elsewhere. The trial follows a two stage sequential multiple assignment random trial SMART trial plan. The trial is split into two 12-week intervention stages with 3 study visits that occurred at the beginning of Stage 1 (Visit 0/Week 0), Stage 2 (Visit 1/Week 12), and the end of Stage 2(Visit 2/Week 24). At baseline (Visit 0/Week 0) participants were randomized to one of four interventions. To participate in the study participants were required to be eligible for a minimum of 3 of the treatments at baseline. A re-randomization happened at Week 12, where participants were assigned to one of four responder status categories using a combination of Week 12 Pain, Enjoyment of Life, and General Activity (PEG) and Patient Global Impression of Change (PGIC) scores. Participants with Week 12 PGIC 1-2 and PEG <= 4 maintained their initial treatment, participant with Week 12 PGIC 1-2 and PEG > 4 were randomized to augment a second treatment, participants with a Week 12 PGIC 3-4 were randomized to either augment a second treatment or switch treatments, and participants with a Week 12 PGIC of 5-7 or participants who could not tolerate their initial treatment were switched to a new treatment. Randomization at the baseline visit was stratified by years of cLBP, depression/anxiety, consent to optional phenotyping, and current use of opioids. The details of the trial are illustrated in the schema below.

#### Schema

#### Sample Size

The sample size calculation for the BEST Trial is based on the ability to accurately estimate the value of the estimated optimal dynamic treatment regime relative to an oracle estimator and is described in the study protocol.

### Statistical Principles

#### Confidence Levels and p-values

Level of statistical significance

Our results will not include any hypothesis testing. All confidence intervals for least squares mean outcome estimates will be reported at the 95% confidence level.

#### Multiplicity Adjustments

We will not use a multiplicity adjustment to adjust for the width of the confidence interval because the least squares mean is not a primary estimand of interest in the trial's statistical design. The primary estimand of interest is the value of the estimated optimal dynamic treatment regime, which is outside the scope of the outcome analysis presented here.

#### Adherence and Protocol Deviations

The analysis will summarize results from all randomized participants. Adherence to interventions will not be considered in this analysis.

#### **Analysis Populations**

The population used for statistical analysis consists of the 805 randomized participants to a Stage 1 treatment.

### **Trial Population**

#### Eligibility

To be eligible for participation in the BEST Trial an individual must meet all of the following inclusion criteria:

- Ability to read and understand English
- Provision of signed and dated informed consent form(s)
- Willing and able to receive study-related messages and survey links via email
- Willing and able to receive study-related phone calls
- Age 18 years old or older
- Low-back pain for at least 3 months and occurring on at least half the days in the past 6 months
- Contraindicated to no more than one of the study interventions at the time of eligibility
- assessment(s)
- Eligible to receive at least three of the four study interventions and willing to receive any
- intervention for which they are eligible
- A PEG score 4 or higher prior to the Run-in period
- Willing and able to undergo required phenotyping as defined in Section 9

- Regular reliable access to an internet-enabled device such as a smart phone, tablet, or laptop
- computer
- Meet Run-in period engagement eligibility criteria:
- Completion of two Run-in study information modules prior to period 1 randomization
- (Visit 0)
- Low-back pain more severe than pain in other parts of the body
- Available to complete the full study protocol (approximately 9 months)

An individual who meets any of the following criteria will be excluded from participation in this study:

- Pregnant at the time of Visit 0 (Baseline)
- Affirmative participant response to any of the following conditions:
  - o Progressive neurodegenerative disease
  - o History of discitis osteomyelitis (spine infection) or spine tumor
  - o BEST Trial Protocol v7.0 20 9/1/2023
  - History of ankylosing spondylitis, rheumatoid arthritis, polymyalgia rheumatica, psoriatic
  - o arthritis, or lupus
  - History of cauda equina syndrome or spinal radiculopathy with functional motor deficit
  - (strength <4/5 on manual motor testing)

  - o Diagnosis of any vertebral fracture in the last 6 months
  - Osteoporosis requiring pharmacologic treatment other than vitamin D, calcium
  - o supplements, or bisphosphonates.
  - o History of any bone-related cancer or cancer that metastasized to the bone
  - o Currently in treatment for any non-skin cancer or plan to start non-skin cancer
  - o treatment in the next 12 months
  - History of any non-skin cancer treatment in the last 24 months
  - Visual or hearing difficulties that would preclude participation
  - Uncontrolled drug/alcohol addiction
  - Individuals actively pursuing disability or workers compensation or involved in active
  - o personal injury-related litigation
  - o Currently participating in another interventional pain study
- Any condition that, in the opinion of the investigator, would preclude the patient from being able to safely participate in in the trial

#### Recruitment

Recruitment for the BEST Trial has been described extensively in the trial protocol and protocol paper.

#### Withdrawal/follow-up

Study flow reporting is specified in Appendix 1.

Timing of withdrawal/lost to follow-up data

Lost to follow-up status was determined at the subsequent study visit at 12-week intervals. Study withdrawal was determined as soon as a participant withdrew consent.

#### **Baseline Characteristics**

List of Baseline Characteristics to be summarized

The baseline characteristics analyzed are:

- Age
- Sex Assigned at Birth
- Gender Identity
- Ethnicity
- Race
- Highest Level of Education Completed
- Current Employment Status
- Current Relationship Status
- Number of People Living in Household
- Annual household income from all sources
- PEG score (0 to 10)
- Self-Reported low-back pain duration (months)
- Self-reported low-back pain duration (category)
- Low-back Pain Frequency in the Past 6 months
- Low-back Pain Specific Pain Intensity
- Ever had a low back operation?
- When was the last back operation?
- Any back operations involve a spinal fusion?
- Ever unemployed for 1 or more months due to low back pain
- Ever file or awarded worker's compensation claim related to back problem
- Involved in a lawsuit or legal claim related to back problem
- Ever applied for, or received, disability insurance for pain condition
- BMI
- Systolic Blood Pressure (mmHg)
- Diastolic Blood Pressure (mmHg)
- Heart Rate (bpm)
- Ever had Hip Replacement surgery?
- Ever had Knee Replacement surgery?
- Observed Gait
- Tobacco Use in Previous 12 Months
- Alcohol Use in Previous 12 Months
- Drug Use in Previous 12 Months
- Prescription Drug Used Not as Intended in Previous 12 Months
- Currently Taking Opioid Medication (daily)
- Previously diagnosed with COVID-19
- Long COVID
- COVID-19 Vaccine

- Fear avoidance beliefs about physical activity raw scoring scale 2
- GAD-2 Raw Score
- Keele STarT Back Screening Tool Risk
- Oswestry Disability Index Percentage
- Pain Catastrophizing Scale SF-6
- Pain Detect Questionnaire Raw Score
- PHQ-2 Raw Score
- HEAL Positive Outlook Raw Score
- PROMIS-Cognitive Function Abilities 2a Raw Score
- General Sensory Sensitivity Score External
- General Sensory Sensitivity Score Interoception
- General Sensory Sensitivity Score Total
- Self-reported Sleep Duration in the Past Month (hours)
- Symptom Severity Index
- Widespread Pain Raw Score
- Stomach Pain in the Past 4 Weeks
- Headaches in the Past 4 Weeks
- Radiating Pain to Buttock/Thigh, Past 2 Weeks
- Radiating Pain to Below Knee, Past 2 Weeks
- Social Determinants of Health: Transportation Needs
- Social Determinants of Health: Healthcare Needs
- Social Determinants of Health: Food Insecurity
- Social Determinants of Health: Food Money
- Social Determinants of Health: Utilities
- Social Determinants of Health: Stable Housing
- Social Determinants of Health: Emotional Support
- Social Determinants of Health: Number of Close Friends
- Perceived Discrimination: Race/Ethnicity
- Perceived Discrimination: Orientation/Gender Identity

#### Details of how baseline characteristics will be summarized

The baseline characteristics are reported as in Appendix 2. Continuous variables are summarized with means and standard deviations. Categorical variables are analyzed with counts and percentages. More details and analysis of the baseline population are described elsewhere.

## **Analysis**

#### **Analysis Methods**

A linear mixed-effect model (LMM) was used to model the least squares mean of the primary and secondary outcomes at Visit 2 (Week 24) by the Stage 1 treatment assignment for all continuous outcomes. Random intercepts and a linear random slope for time were included to account for subject-level variability. The randomization and minimization algorithm variables are included as

fixed effects. Week indicators as fixed effects were included to model non-linear effects of time. An additional fixed effect was included for the number of treatments a participant was eligible for at the baseline visit. Estimation was conducted using REML and modern optimization approaches with the lme4 package in R. Least squares means were estimated for each Week 24 outcome, along with associated 95% confidence intervals, using the emmeans package in R. Due to the small number of participants on opioids in the BEST Trial sample, we only report counts of participants self-reporting opioid use at Week 24.

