Pain, Enjoyment of Life, and General Activity (PEG) and Patient Global Impressions Scale (PGIC) will be assessed at 6 weeks (midpoint of intervention period one), 12 weeks (Visit 1), 18 weeks (midpoint of intervention period two), 24 weeks (Visit 2), and 36 weeks post-baseline (12 weeks after intervention period two). Basic safety assessments will also be performed at these time points to assess participant tolerability to their current study intervention(s). Patients who are unable to tolerate their assigned study treatment will be educated on how to safely discontinue their current treatment plan but will otherwise remain in the study.

Objectives:

The primary objective is to estimate an algorithm to assign sequences of two cLBP treatments based on phenotypic markers and an individual patient's response to the initial treatment (*i.e.*, a dynamic treatment regime (DTR)) that optimizes effectiveness. as characterized by the primary and secondary endpoints.

The study has the following three secondary objectives:

- Estimate DTRs that optimally balance multiple outcomes, taking into account participant preferences for outcomes including pain intensity, pain interference, physical function, opioid use, depression, anxiety, sleep duration and sleep disturbance.
- Estimate DTRs that incorporate additional phenotypic markers (i.e., deep phenotyping) collected on a subset of participants.
- Assess whether effectiveness is sustained on outcomes collected
 24 weeks after randomization to the second treatment.

Analyses for secondary objectives will utilize the set of primary and secondary endpoints.

The study has the following exploratory objectives:

- Evaluate the comparative effectiveness of individual treatments.
- Evaluate the comparative effectiveness of different treatment regimes (i.e., a particular regime with a given set of rules at each decision point).
- Evaluate the impact of treatment order on outcomes.

Analyses for exploratory objectives will utilize the set of primary and secondary endpoints.

The primary endpoint for the study is 24-week change from baseline in patient-reported pain intensity and interference, measured with the Pain, Enjoyment of Life, and General Activity (PEG) scale.

Secondary endpoints are:

- 24-week change from baseline in pain interference, measured with the 4-item PROMIS Pain Interference scale (PROMIS-PI, 4a)
- Incidence of any opioid use at 24 weeks post baseline.

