#### **Missing Data**

We assume the data are missing at random. We include all subjects randomized at baseline in the analysis, regardless of the number of future observations. There is no missingness in model covariates because they were required for randomization at the baseline visit.

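### The SAP's mixed model specifies no adjustment for the Visit 0 value of the outcome; a common baseline mean should be written in

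*SAP*

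**What the plan says.** SAP, Analysis Methods, fits a linear mixed model to each of the seven continuous outcomes.

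- **Random part:** "Random intercepts and a linear random slope for time were included to account for subject-level variability".
- **Fixed part:** "The randomization and minimization algorithm variables are included as" fixed effects. Also "Week indicators as fixed effects were included to model non-linear effects of time", and "An additional fixed effect was included for the number of treatments a participant was eligible for at the baseline visit". Stage 1 arm is the factor reported on.
- **Output:** "Least squares means were estimated for each Week 24 outcome, along with associated 95% confidence intervals, using the emmeans package in R".

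The balancing factors are given in SAP, Trial/Study Design: "Randomization at the baseline visit was stratified by years of cLBP, depression/anxiety, consent to optional phenotyping, and current use of opioids". Protocol 10.4.4 lists the same four, each with two levels. None is a Visit 0 PEG, PROMIS or sleep value.

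SAP, Missing Data, states: "There is no missingness in model covariates because they were required for randomization at the baseline visit". The same section keeps every randomized participant in the model, however few follow-up observations that person has.

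On the endpoint, Protocol 4.1 says: "The primary endpoint for the study is 24-week change from baseline in patient-reported pain intensity and interference". In SAP, Outcome Definitions, the timing column names the Week 24 score. The ranges are those of a change: pain interference runs from −34 to 34 on a T-score running from 41.6 to 75.6 (75.6 − 41.6 = 34.0).

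The SAP does not say whether the response is the score or the change, whether Week 0 is a response, whether arm is crossed with week, or whether the arms share a baseline mean.

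**The concern.** The baseline score is usually among the strongest predictors of the same score later. A model that leaves it out lets a chance difference between arms at Visit 0 pass into the Week 24 arm means, and for a Week 24 score or a plain change score it gives wider intervals than the collected data allow. The minimization factors do little to prevent this. Two-level depression/anxiety status is only a coarse stand-in for two secondary outcomes, and nothing balances PEG directly.

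These arm means and their 95% intervals are the efficacy results this SAP delivers for the continuous outcomes. Readers will set the four arms side by side even though no test is planned.

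**Working it through.** **The plan's own figures.** The documents give no SD, correlation or expected interval width for this model, so there is no model figure to reproduce. The one checkable design figure is the randomized sample size in Protocol 13.2: 630 / 0.85 = 741 and 820 × 0.9 = 738, both in line with about 740. It comes from the treatment-regime simulation and does not depend on the mixed model.

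**Inputs.**
- Randomized: 805 (SAP, Analysis Populations), about 201 per arm.
- Re-randomized at Week 12: 683 (SAP, Appendix 3), about 171 per arm, used as a stand-in for the number with Week 24 data.
- SD: set to 1 at both times (assumption; Protocol 13.2 works on a standardized scale).
- Correlation r between Visit 0 and Week 24: 0.3 to 0.6 (assumption; not in the documents).
- Complete data.

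**Step 1. Carry-over of a chance baseline difference D.** With equal SDs, the Week 24 difference is expected to move by rD.
- Week 24 score, free arm-by-week means: carry-over r. With complete data, making Week 0 a response and adding random intercepts and slopes does not change this.
- Change score without a baseline covariate: rD − D, so carry-over is −(1 − r).
- Common baseline mean, or baseline as a covariate: rD − rD = 0.
- Arm as a main effect only, Week 0 among k equally correlated visits: the estimate averages all visits, so carry-over is (1 + (k − 1)r)/k. For PEG at Weeks 0, 6, 12, 18 and 24 (k = 5) this is 0.44 at r = 0.3 and 0.68 at r = 0.6. The estimate is then not specific to Week 24.

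The SD of D between two arms of 201 is √(2/201) = 0.0997, so its 95% range is ±0.195 SD. At that limit the carry-over is r × 0.195 = 0.06 to 0.12 SD for the score, or −(1 − r) × 0.195 = −0.14 to −0.08 SD for the change.

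**Step 2. Precision of a between-arm difference.** Variances, in units of 2/n: raw score 1; change 2(1 − r); adjusted 1 − r². The SE ratio of adjusted to raw is √(1 − r²). The SE ratio of adjusted to change is √((1 − r²)/(2(1 − r))) = √((1 + r)/2).

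**Step 3. Precision of one arm mean.** With a baseline mean pooled over four equal arms, the adjusted variance is (1 − r²) + r²/4 = 1 − 0.75r² of the raw-score variance.

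| r | Adjusted / raw, difference | Adjusted / change, difference | Adjusted / raw, arm mean |
|---|---|---|---|
| 0.3 | 0.954 | 0.806 | 0.966 |
| 0.4 | 0.917 | 0.837 | 0.938 |
| 0.5 | 0.866 | 0.866 | 0.901 |
| 0.6 | 0.800 | 0.894 | 0.854 |

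At 171 per arm, the SE of a difference is 0.108 SD for the raw score. Adjusted, it is 0.103 SD at r = 0.3 and 0.087 SD at r = 0.6. For the change score it is 0.128 and 0.097 SD.

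**The case against.** The strongest reply is that the model may already adjust. A participant with no follow-up can contribute only if Week 0 is a response, and SAP, Missing Data, keeps such participants. If the arms share one mean at Week 0, baseline is fully adjusted for and no baseline covariate would be listed. This stands: a reader might infer from the list of fixed effects that the model never adjusts, and the documents do not establish that. They neither state nor exclude a common baseline mean. It is, however, a deliberate parameterization, and a SAP that itemises the number of eligible treatments would be expected to mention it.

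Three further points stand.

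- The issue is not separate from the arm-by-week structure. Once Week 0 is a response, the way arm and week are crossed decides whether baseline is adjusted for.
- A reader might infer that an arm starting worse by chance must look worse at Week 24. That holds for a score; for an unadjusted change score the sign reverses. If arm is a main effect only, neither SE ratio for a difference applies, and that estimate can even have a smaller SE because it averages over visits.
- The consequence is limited. SAP, Confidence Levels and p-values, plans no tests, and SAP, Multiplicity Adjustments, says the least squares mean is not a primary estimand. Chance imbalance under randomization is not bias in expectation, and baseline PEG will be tabulated by arm.

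None of this supplies the missing specification.

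**Conclusion.** The point holds in this form: the SAP specifies no adjustment for the Visit 0 value of the outcome, and unless an unstated common baseline mean was used, chance baseline imbalance reaches the Week 24 arm comparison. The share carried over is about r for a score with free arm means and −(1 − r) for a plain change score.

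For r of 0.3 to 0.6, adjustment would reduce the SE of a between-arm difference by 5–20% against the raw score, or by about 19–11% against the change score. It would reduce the SE of a reported arm mean by about 3–15% against the raw score. The between-arm figures concern comparisons that readers will make, not estimates the SAP plans to report.

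These sizes rest on the assumed r, equal SDs at both times and complete data. They are not converted to PEG points, because the documents give no SD on that scale. A reader might infer that the trial's main conclusion is weakened. It is not: the dynamic treatment regime objective and its sample size do not use this model.

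**What to change.** In SAP, Analysis Methods, state that the response is the score and that Week 0 is one of the responses. Fit one Week 0 mean common to all four arms, and include arm-by-week effects only at post-baseline weeks. This keeps all 805 randomized participants, as SAP, Missing Data, requires. Change from baseline can still be reported as the Week 24 arm mean minus the common baseline mean, with the same arm contrasts. Align the Outcome Definitions table with this choice. If a common baseline mean was already used, saying so is enough.

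Adding the Visit 0 value as a covariate is an alternative, but not an equivalent one. Participants with no follow-up would drop out of the model, and the statement that no covariate is missing would need revisiting, because PROMIS and sleep values are not among the factors listed for randomization.

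The cost is a revised model statement and a refit of seven outcomes. The Visit 0 values are already scheduled, so no new data are needed.

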6. OBJECTIVES AND ENDPOINTS

The BEST Trial will inform a precision medicine approach to cLBP and is designed to identify treatments that are most effective in identifiable subgroups of patients. Therefore, the study was designed to estimate dynamic treatment regimes rather than to test the overall effectiveness of any single intervention or combination of interventions.

The primary objective is to estimate an algorithm to assign sequences of two cLBP treatments based on phenotypic markers and an individual patient's response to the initial treatment (*i.e.*, a dynamic treatment regime) that optimizes effectiveness.

In this trial, phenotypic markers will not be used to assign treatments, rather participants will be randomly assigned to treatment. Response to initial treatment will guide second-stage randomization and will be assessed with the Pain, Enjoyment of Life, and General Activity (PEG) scale and the Patient

Global Impression of Change (PGIC) 12 weeks after the first randomization. The primary analysis will then estimate an algorithm that can be applied to *cLBP* patients that will optimally assign treatments based on a patient's phenotypic markers and changing response (a dynamic treatment regime or DTR). Phenotypic markers that will be considered include, for example, preference for treatment and outcome priorities, history of depression, and time since diagnosis of chronic back pain. Study participant phenotypic markers will be assessed at baseline and a subset will be measured at the end of the first intervention period. As part of this analysis, we will compare the estimated best DTR that does *not* use phenotypic variables or participant response with the estimated *optimal* DTR. A hypothetical example of a DTR that we might estimate would involve a sequence of two decision rules: Individuals with chronic low-back pain receive physical therapy for 12 weeks and if pain intensity and interference are below a given threshold, continue regular follow up with patient; if pain interference is over the threshold, provide patient with prescription for duloxetine for 12 weeks.

This procedure will be applied to the following primary and secondary endpoints:

- Primary endpoint: 24-week change from baseline in patient-reported pain intensity and interference, measured with the Pain, Enjoyment of Life, and General Activity (PEG) scale at Visits 0 (baseline) and 2 (24 weeks of treatment)

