#### Objectives

The BEST trial was powered for the study's primary objective of estimating an algorithm to assign sequences of two cLBP treatments based on phenotypic markers and an individual patient's response to the initial treatment (i.e., a dynamic treatment regime (DTR)) that optimizes effectiveness, as characterized by the primary and secondary endpoints. In this outcome analysis, we will report the ITT-least squares adjusted mean of the 24-week outcomes of the BEST Trial and associated 95% confidence intervals. It is important to reiterate that the BEST trial was powered for biomarker discovery. This analysis describes the primary and secondary outcomes of the study.

[figure not shown]
In this analysis, we aim to:

- Report on BEST Trial study flow, baseline characteristics, and adverse events
- Estimate 24-week least squares means for study outcomes by Stage 1 treatment assignment.

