#### **Outcome Definitions**

Outcome	Outcome Type	Specification	Specific	Calculation to	Analysis
Name	(primary/secondary)	of outcome	measurement	derive	Method
		and timing	and units	outcome	
Patient-	Primary	PEG Score	The PEG scale	Calculate the	LMM
Reported		measured at	is based on a	PEG Score by	
Pain		the Visit 2	participant	averaging the	
Intensity		(Week 24)	rating of their	responses	
and			pain in 3	from each of	
Interference			areas: pain	the 3 scales.	
Score			intensity, pain		
			interference		
			with		
			enjoyment of		
			life, and pain		
			interference		
			with general		
			activities. A		
			rating is given		
			ranging from -		
			10 (lowest) to		
			10 (highest)		
			on each of		
			these scales.		
			We use the		
			average of		
			these ratings,		
			with higher scores		
			indicating		
			increased		
			pain intensity		
			and		
			interference		
			at 24 Weeks		
			compared to		
			Baseline.		
Pain	Secondary	Pain	Ratings of the	Calculate the	LMM
Interference		Interference	consequences	raw score by	

		at Visit 2 (Week 24)	of pain on relevant aspects of one's life. This includes the extent to which the pain hinders engagement with social, cognitive, emotional, physical, and recreational activities. Results range from -34 to 34 (t-scores range from 41.6 to 75.6), with higher scores indicating increased pain interference at 24 Weeks compared to	summing all appropriate responses, then translate the raw score to the corresponding T-Score	
Physical Function	Secondary	Physical Function at Visit 2 (Week 24)	Baseline.  Measured by the PROMIS-PF Short Form 6b. The PROMIS-PF Short Form 6b is a series of 6 questions.  Results range from -37.1 to 37.1 (t-scores range from 21.6 to 58.7), with higher scores indicating increased physical functioning at 24 Weeks	Calculate the raw score by summing all appropriate responses, then translate the raw score to the corresponding T-Score	LMM

			compared to Baseline.		

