Depression Score	Secondary	Depression at Visit 2 (Week 24)	Measured by the PROMIS 4-item depression scale from the PROMIS 29 profile. The PROMIS 4-item depression scale from the PROMIS 29 profile is a series of 4 questions. A rating of negative mood, views of self, as well as decreased positive affect and engagement. Results range from -38.4 to 38.4 (t-scores range from 41.0 to 79.4), with higher scores indicating increased depression at 24 Weeks compared to Baseline.	Calculate the raw score by summing all appropriate responses, then translate the raw score to the corresponding T-Score	LMM
Anxiety Score	Secondary	Anxiety at Visit 2 (Week 24)	Measured by the PROMIS Emotional Distress-Anxiety scale (PROMIS-EDA 4a). The PROMIS-EDA 4a is a series of 4 questions. A rating of fear, anxious	Calculate the raw score by summing all appropriate responses, then translate the raw score to the corresponding T-Score	LMM

	T	T	1 .	Τ	 
			misery,		
			hyperarousal,		
			and somatic		
			symptoms		
			related to		
			arousal.		
			Results range		
			from -41.3 to		
			41.3 (t-scores		
			range from		
			40.3 to 81.6),		
			with higher		
			scores		
			indicating		
			increased		
			anxiety at 24		
			Weeks		
			compared to		
			Baseline.		
Sleep	Secondary	Sleep	Measured by	Calculate the	LMM
Disturbance		Disturbance	the PROMIS	raw score by	
		at Visit 2	short form 6a.	summing all	
		(week 24)	The PROMIS	appropriate	
			short form 6a	responses,	
			is a series of 6	then translate	
			questions. A	the raw score	
			rating of sleep	to the	
			quality, sleep	corresponding	
			depth, and	T-Score	
			restoration	1 55515	
			associated		
			with sleep.		
			Results range		
			from -44.4 to		
			44.4 (t-scores		
			range from		
			31.7 to 76.1),		
			with higher		
			scores		
			indicating		
			increased		
			sleep		
			disturbance at		
			24 Weeks		
			compared to		
			Baseline.		
Sleep	Secondary	Response to	Response to		LMM
Duration		BACPAC	"During the		
		sleep	past month,		
		disturbance	how many		
	1	aistai balltt	110 w many	I	

		question at Visit 2 (Week 24)	hours and minutes of actual sleep did you get at night?" measured in Hours and Minutes. Results range from -24 to 24 hours, with higher number of hours indicating increased sleep duration at 24 Weeks compared to Baseline.	

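### The SAP's mixed model lists no Stage 1 arm-by-week term, so its by-arm Week 24 means carry an arm effect averaged over visits; the outcome table also mixes levels with changes from baseline.

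*SAP*

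**What the plan says.** The SAP's Objectives set the target: "Estimate 24-week least squares means for study outcomes by Stage 1 treatment assignment". Under Analysis Methods, the continuous outcomes go into a linear mixed model. The terms listed are a subject-level random intercept and linear slope, the randomization and minimization variables, the number of treatments the participant was eligible for, and time: "Week indicators as fixed effects were included to model non-linear effects of time". The output is then described: "Least squares means were estimated for each Week 24 outcome, along with associated 95% confidence intervals, using the emmeans package in R". There is no interaction between arm and week and no model formula. The SAP does not say which weeks enter, or whether Week 0 is a response or a covariate. The Missing Data section says "We include all subjects randomized at baseline in the analysis, regardless of the number of future observations", which suggests that Week 0 is a response row.

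The Outcome Definitions table specifies each outcome at Visit 2. PEG is derived as an average and the PROMIS scales as T-scores, with no subtraction of baseline. The same rows give ranges symmetric about zero. For physical function: "Results range from -37.1 to 37.1 (t-scores range from 21.6 to 58.7". For sleep duration, where the derivation cell is empty: "Results range from -24 to 24 hours, with higher number of hours indicating increased sleep duration at 24 Weeks compared to Baseline". PEG items are said to run from -10 to 10. Protocol section 12.1 scores them 0 to 10, and section 6 defines the endpoint as a change: "Primary endpoint: 24-week change from baseline in patient-reported pain intensity and interference".

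**The concern.** In an additive model, asking for the mean at Week 24 moves all arms to the Week 24 time level and leaves the gap between them unchanged. That gap is estimated from all modelled visits together. The random slope does not help: it has mean zero across participants and is not arm-specific.

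A constant gap conflicts with the design. At Week 0 the expected arm difference is zero by randomization. At Week 12 participants are assigned to maintain, augment or switch (protocol section 7.1), so Stage 1 contrasts can be expected to change afterwards. The by-arm means are the outcome result this SAP promises. As listed, the differences between them can be too small or too large, and the intervals are not Week 24 intervals.

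The table adds a second ambiguity: a reader cannot tell whether the reported figure is a score or a change.

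**Working it through.** **Outcome table.** For each PROMIS row, maximum minus minimum of the stated T-score range:

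- Pain interference: 75.6 - 41.6 = 34.0 (stated ±34)
- Physical function: 58.7 - 21.6 = 37.1 (stated ±37.1)
- Depression: 79.4 - 41.0 = 38.4 (stated ±38.4)
- Anxiety: 81.6 - 40.3 = 41.3 (stated ±41.3)
- Sleep disturbance: 76.1 - 31.7 = 44.4 (stated ±44.4)

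All five match exactly, as do PEG (10 - 0 = 10) and sleep duration (24 - 0 = 24). The printed ranges are therefore change ranges, while the derivations give levels. A pain-interference level is at least 41.6 and cannot lie within ±34; a depression level is at least 41.0 and cannot lie within ±38.4.

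**What the listed model estimates.** Write δ(t) for the true arm difference at visit t and V for the covariance of a participant's visits under a random intercept and slope. With balanced data the additive model's single arm difference is w'δ, where w = V⁻¹1 / (1'V⁻¹1).

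Assumed inputs, since the documents give none: intercept SD 1.5, residual SD 1.2, slope SD 0 to 0.08 per week, intercept–slope correlation -0.3 to 0.2. PEG visits are Weeks 0, 6, 12, 18 and 24 (protocol section 7.1, leaving out Week 36).

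- No slope variance: each visit has weight 0.20.
- Slope SD 0.04, correlation 0: weights 0.31, 0.26, 0.20, 0.14, 0.09. Week 0 counts more than three times as much as Week 24.

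Worked example with the second set and a linearly growing effect: 0.26×0.25 + 0.20×0.50 + 0.14×0.75 + 0.09×1 = 0.36, so about 36% of the Week 24 difference is returned.

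Share of the true Week 24 difference returned over the full range of assumptions:

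| Effect at Weeks 0, 6, 12, 18, 24 | Week 0 a response | Week 0 not a response |
|---|---|---|
| Full from Week 12: 0, 0.5, 1, 1, 1 | 30–74% | 67–88% |
| Linear: 0, 0.25, 0.5, 0.75, 1 | 10–54% | 28–64% |
| Fades to half: 0, 0.5, 1, 0.75, 0.5 | 70–114% | 137–144% |
| Fades to a third: 0, 0.5, 1, 0.67, 0.33 | 110–154% | 186–222% |

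An effect that is constant from Week 6 is returned in full only if Week 0 is not a response. With Week 0 included and equal weights it is 1 - 0.20 = 80%.

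**In PEG points.** Protocol section 13.2 assumes effect sizes of 0.4 for the exercise and manual therapy arm and 0.1 for enhanced self-care. With an assumed SD of 2, the difference is (0.4 - 0.1) × 2 = 0.60. With Week 0 as a response it is returned as 0.18–0.44 if full from Week 12, or 0.06–0.32 if linear. If it peaks at 0.60 and fades to 0.20, it is returned as 0.22–0.31.

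**Simulation check.** REML fits with 805 participants, 40 replicates, a linear build-up to a true difference of 0.30 SD, and assumed SDs of 0.7 (intercept), 0.8 (slope per 24 weeks) and 0.5 (residual):

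| Visits | Additive (SE) | With arm-by-week | Additive 95% CI covers 0.30 |
|---|---|---|---|
| 0, 6, 12, 18, 24 | 0.04 (0.08) | 0.27 | 5% |
| 0, 12, 24 | 0.06 (0.08) | 0.29 | 20% |

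**The case against.** The strongest reply is that the SAP text is a prose summary, not a formula, and the fitted code may contain the interaction. That is possible, and printing the formula would settle it. As written, though, the plan does not specify the analysis it promises.

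Second, the sizes depend on choices the SAP leaves open. If change were the response, Week 0 would be zero by construction, and the right-hand column of the first table is the nearer guide. Adding Week 36, with effects held after Week 24, gives 36–78% (full from Week 12) and 12–62% (linear). The schedule of activities has the PROMIS scales at Weeks 0, 12 and 24, plus Week 36. On Weeks 0, 12 and 24 the shares are 30–70% and 13–53%; without Week 0, an effect full from Week 12 is returned in full. These points change the size, not the defect.

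Third, the SAP plans no between-arm contrasts, and the pair used above is the most extreme. The average of the four assumed effects is (0.1 + 0.25 + 0.3 + 0.4)/4 = 0.2625. At SD 2 and 10% returned, the arm means are therefore displaced by at most 0.9 × 2 × the distance from 0.2625. That is 0.29 (self-care), 0.25 (exercise and manual therapy), 0.07 (duloxetine) and 0.02 (ACT) PEG points. The standard error of one arm's mean with about 200 participants and no slope variance is √((1.5² + 1.2²)/200) = 0.14. So two arms are displaced by more than sampling error in the worst build-up case, and two hardly at all.

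Fourth, the analysis is descriptive: no tests are planned, and the SAP notes that "the least squares mean is not a primary estimand of interest in the trial's statistical design". This stands and limits the consequence.

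On the table, each PROMIS row does print both ranges, and the SAP's baseline list gives PEG as 0 to 10. The missing subtraction step and the wrong PEG item range remain.

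**Conclusion.** The plan is wrong as written on both counts. Fitted as listed, the model gives by-arm Week 24 means whose differences are visit-averaged. Depending on the time profile, the listed model returns from 10% to 154% of the true Week 24 PEG difference with Week 0 as a response, and from 28% to 222% without it. These figures rest on assumed variances and profiles. The direction of error depends on the profile, so a reader cannot correct for it. The level/change conflict and the PEG item range can be read directly from the documents and need no assumption.

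The all-arm Week 24 mean, the dynamic treatment regime analysis and the sample size are not affected. Opioid use is reported as counts and is also unaffected.

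**What to change.** Keep the score at each visit as the response, with Week 0 included, and add Stage 1 arm by week, optionally with a common baseline mean across arms. Report by arm the model-based Week 24 minus Week 0 contrast with its 95% confidence interval, which is the protocol's endpoint, and give the Week 24 level in support. Do not replace the response with a single Visit 2 minus Visit 0 value: that leaves one value per participant and drops everyone without Visit 2.

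Print the model formula and the weeks that enter. If the fitted code already held the interaction, printing the formula is enough for the model part. In the outcome table, state PEG items as 0 to 10 and label each range as level or change, to match what is reported.

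The cost is SAP wording and a refit on existing data. The SAP describes the fit in the past tense, so a refit should be labelled as made after the first analysis. Under the assumptions above, the standard error of the between-arm difference in change becomes about 1.1–1.6 times that of the additive model, or about 1.0–1.5 times with a common baseline mean.
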